5. STUDY VISITS AND PROCEDURES

5.1. Schedule of Visits

A **screening (Visit -1)** session will be conducted. This could take place after a routine clinic visit, or by phone, to perform the Informed Consent (IFC) discussion, review inclusion criteria, collect demographics and basic medical history, and begin MRI safety screening. The Language Battery will also be completed as part of the screening visit. Additionally (in the case of those meeting criteria), patients might visit the Tosa Health Center or Medical College of Wisconsin for stimulation planning. This would entail the use of a Transcranial Magnetic Stimulation (TMS) neuronavigation system. The Language battery and TMS can occur on two separate days prior to the first treatment visit of Treatment Period 1. Subjects will also be invited to **baseline (Visit 1)**. At baseline, the study team will complete fMRI and MEG scans and randomize participants to a treatment group. Procedures within Visit -1 and Visit 1 may be completed in any reasonable order, and may overlap, up to 3 months prior to the first treatment visit of Treatment Period 1. At **Visit 1**, subjects will receive tDCS while simultaneously completing the reading and repetition “trained tasks. Subjects will then return for 9 additional **treatment sessions (Visits 2-10)** where they will receive stimulation or sham, along with trained task administration. At **Visit 10**, subjects will receive MRI, MEG scans, and the Language Battery. These procedures may be completed one month after the last treatment session of Treatment Period 1. At 8-weeks from the last Treatment Period 1 visit, subjects will return for the first **assessment session (Visit 11)**, in which the Language battery, including the trained tasks will be repeated. Subjects will then return 8 weeks later to begin the second series of treatments (**Treatment Period 2, Visits 12-21**) and receive MRI, MEG, and Language Battery on visits 12 and 21. MRI, MEG, and the Language battery will be completed no greater than 3 months prior to the first treatment session of Treatment Period 2, then again no greater than one month after the final treatment session of Treatment Period 2. At each visit during Treatment Period 2, subjects will receive the cross-over treatment (either sham or stimulation) while simultaneously completing the reading and non-word trained tasks. The final

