6. DATA MANAGEMENT

6.1. A secure web-based system will be used to enroll patients and obtain the randomly assigned treatment group. Data forms will be printed, completed, and entered into the database using a secure web-based application. The database will be monitored for completeness, consistency, accuracy, and timeliness. No patient-identifying information will be stored in the database. To ensure that data are secure from external violation, computer systems containing study data will be password protected, and physical access to the computer systems will be limited.

6.2. Determination of changes in Language Function and Concurrent Improvement in Network Activity.

The language and MRI/rfMRI datasets will be obtained at baseline (before sham/active tDCS administration) and on the last day of each 2-week treatment period. These two time points will be denoted $t = 1, 2$. The two 10-

subject groups, both of which will receive both sham and active tDCS at different treatment phase, will be denoted $g = 1, 2$. The set of Language (LG) scores for subject s , from group g , at time t will be denoted $LG(s, g, t)$, where $s = 1, \dots, 10$; $g = 1, 2$; and $t = 1, 2$. The Language-Network functional connectivity (LFC) calculated between the left posterior temporal and inferior parietal cortex for subject s , from group g , at time t will be denoted $LFC(s, g, t)$.

6.3. Language Changes Due to Stimulation. Scores across all tests within the language battery will be combined into one composite measure to facilitate assessment of overall language performance across domains. All seven scores will be normalized to a Z-score by transforming individual raw test scores according to the mean and standard deviation of the scores for all subjects. Then, Z-scores of each test will be averaged to obtain an individual composite language Z-score (McConahey et al., 2017). We will employ age, years of education, gender, and gray matter (GM) volume as time-invariant covariates to obtain residual variables to determine the LG changes due to stimulation. We will model the LG score as a function of these nuisance regressors. This regression will be performed using all the data (i.e., all subjects, all groups, and all times):

$$\Delta LG(s, g, t) = \beta_0 + \beta_1 Age(s) + \beta_2 Edu(s) + \beta_3 GM(s) + \beta_4 Gender(s) + Res(s, g, t)$$

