The rsMEG datasets will be obtained at baseline (before sham/active tDCS administration) and on the last day of each 2-week treatment period. For data analysis we will use the well established Epilepsy Connectome Project (ECP) MEG methods, currently used at MCW. A scalp digitization will be generated during each session of the MEG procedure that includes anatomical landmarks and localizer coils. The MEG data will be co-registered to the MRI using a minimization of the distance from the digitized headshape to the MRI derived scalp surface. The localizer coils will provide the position of the patients head relative to the MEG sensors. Sensor level activity will be projected to the cortical surface using minimum norm based spatial filters with anatomical priors. The cortical surface will be downsampled to approximately 8000 vertices; the orientation and location will act as priors on solving the transformation from sensor space to source space, known as the inverse solution. Data from the cortical surface will be spatially averaged over the anatomical parcellations. These parcellated timeseries will be used to calculate band-limited connectivity measures. Targeted exploration of connectivity driven by current understanding of the pathophysiology of lvPPA will also be pursued.

Connectivity between all ROI-pairs will be calculated in the theta (4-8 Hz), alpha (8-12 Hz), beta (13-30 Hz), and low-gamma (30-55 Hz) frequency bands using three different metrics: coherence (COH), phase lag index (PLI), and debiased weighted phase lag index (d-wPLI). Mean connection strengths within 3 intra-hemispheric language-specific ROI-groups, and those between all intra-hemispheric ROIs will be computed. We will also compute mean connection strengths between language ROI-groups and all remaining brain ROIs, and those between each hemispheric ROI and all other brain ROIs.

The same multiple linear regression models used for the analysis of rsfMRI data will be used for the analysis of rsMEG data (for simplicity, regression equations are not shown). See above for details.

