7.10. Feedback Mechanism

Evaluation and response to any subject complaints will be reviewed by the DSMB. The IRB will be notified of protocols violations and emergence of unexpected AEs at any time during the study. In addition, a report by the DSMB will be provided to the IRB at the end of the study.

Table 1. Schedule of Study Procedures.

Period	Screen	Treatment Period 1			Assessment 1 ^{ab}	Treatment Period 2			Assessment 2 ^b
Visit	-1	1	2-9	10	11	12	13-20	21	22
Visit window	-3 months	-3 months	+1 month	+1 month	±1 month	-3 months	+1 month	+1 month	±1 month
Informed Consent	X								
Inclusion/Exclusion Criteria	X								
Demographics	X								
Medical History	X								
MRI Safety Screening	X					X			
Language Battery	X ^j		X ^{fh}		X	X ⁱ		X ^{fh}	X
Training Tasks		X	X	X	X	X	X	X	X
fMRI ^c		X ^g		X ^h		X ⁱ		X ^h	
MEG		X ^g		X ^h		X ⁱ		X ^h	
Randomization		X							
tDCS		X	X	X		X	X	X	
Phone Follow Up/					X				

Visit Reminder ^d									
Adverse Events ^d		X	X	X	X	X	X	X	X
TMS Neuronavigation (for stimulation planning) ^e	X ^j								

^a Assessment 1, Visit 11 occurs in the middle of the 16-week washout period.

^b In the case of early termination, Assessment Visit procedures will be performed.

^c Subjects will undergo mock scanner training. If a subject has been previously engaged in MRI as part of research, the subject may be excused from mock scanner training.

^d Phone Follow-Ups will be conducted during the 16-week washout period. They will be conducted 4 weeks post Treatment Period 1, 1 week prior to Assessment Visit 1, and 1 week prior to Treatment Period 2. AE review will be completed, and reminders for upcoming visits provided.

^e TMS Neuronavigation will occur at the investigators discretion.

^f Language assessment sessions will be conducted after Treatment periods 1 and 2 (visit 10 for period 1 and visit 21 for period 2).

^g These procedures can occur on 2 or more separate days, but within 3 months before the first treatment session of Treatment Period 1. They may overlap with Visit -1 procedures.

^h These procedures can occur on 2 or more separate days, but within 1 month after the last treatment session of Treatment Period 1 or the last treatment session of Treatment Period 2.

ⁱ These procedures can occur on 2 or more separate days, but within 3 months before the first treatment session of Treatment Period 2.

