Study Title: High-Definition Transcranial Direct Current Stimulation (HD-tDCS) in logopenic variant Primary Progressive Aphasia (lvPPA): Effects on Language and Neural Mechanisms.

NCT: NCT03805659

Date of document: July 06, 2023

Statistical Analysis:

- The small sample size in this study precluded group-level statistical analysis.
- Instead focused on a within subject item-level analysis.
- Language performances in each trial period were assessed separately to help control for potential carryover effects and for effects of progressive neurodegeneration.
- The Cochran's Q test was used to determine if there were any differences on a dichotomous variable across the three-trial period timepoints.
- Because the same assessment list/version was used within a given stimulation condition per participant, we coded "right" and "wrong" answers to an individual assessment item as our dichotomous variable.
- If the preliminary Cochran's Q test demonstrated a significant difference ($p<0.05$) between participant responses in a language assessment between two timepoints, a follow-up non-parametric pairwise comparison between the baseline and timepoint list was tested using a McNemar test with a false discovery rate correction (Sheppard et al., 2021; Hung et al., 2017; Tsapkini et al., 2015).
- While the Cochran's Q and post-hoc McNemar test allowed us an objective comparison between timepoints within conditions for each individual participant, we utilized a Wilcoxon-signed rank test to assess participant performance changes between aHD-tDCS and sHD-tDCS (ex: aHD-tDCS T0-T1 percentage change from baseline vs. sHD-tDCS T0-T1 percentage change from baseline). This assessment would allow us a more quantitative direct comparison between treatment conditions on an individual participant (Sheppard et al., 2021). The statistical analyses described were performed using SPSS version 27.0 (IBM, Armonk NY). A p-value of <0.05 was used to describe statistical significance.

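### The post-treatment measurement is set for the last day of each period in the analysis section but may be taken up to a month later, separately in each period, so its timing can differ by about 30 days within one active-sham comparison.

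*Protocol*

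**What the plan says.** The Protocol gives two accounts of when the post-treatment data are collected.

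- **Analysis sections.** Section 6.2 sets the language and MRI datasets at baseline "and on the last day of each 2-week treatment period". Section 6.6 repeats this for MEG: "The rsMEG datasets will be obtained at baseline (before sham/active tDCS administration) and on the last day of each 2-week treatment period". Section 1.3 gives all three outcomes a time frame of 2 weeks.
- **Visit schedule.** Section 5.1 says that at Visit 10 "subjects will receive MRI, MEG scans, and the Language Battery", and then adds: "These procedures may be completed one month after the last treatment session of Treatment Period 1". For Period 2 the same procedures are repeated before treatment, "then again no greater than one month after the final treatment session of Treatment Period 2". Table 1 footnote h covers both periods and lets the procedures be spread over two or more days, "but within 1 month after the last treatment session of Treatment Period 1 or the last treatment session of Treatment Period 2".

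Visits 11 and 22 are set at 8 weeks after the last treatment visit of their period, with a window of plus or minus 1 month in Table 1.

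The SAP compares the two conditions within a participant by a Wilcoxon signed-rank test on change from baseline ("ex: aHD-tDCS T0-T1 percentage change from baseline vs. sHD-tDCS T0-T1 percentage change from baseline"). It gives no day for T1. Neither document requires the same delay in both periods or adjusts for the actual day of assessment.

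**The concern.** The active-sham contrast sets one T0-T1 change against another in the same person. It is a clean comparison only if T1 means the same thing in both periods. Both conditions include training, so some gain is plausible under sham as well as active, and part of it may fade after the last session. If T1 is taken on the last day in one period and a month later in the other, the contrast mixes stimulation with time since training. A difference can then appear without any stimulation effect, or a real one can be hidden. All of these dates are permitted, so nothing would be recorded as a deviation.

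The design has little protection against this. The SAP says that the small sample ruled out group-level analysis and that inference is within subject. It also assesses the trial periods separately to help control for carryover and progressive degeneration, which shows that elapsed time is regarded as relevant.

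**Working it through.** **Check of the timeline.** The Protocol Summary gives 2 weeks of treatment, 16 weeks of washout, 2 weeks of treatment and 8 weeks to the final assessment: 2 + 16 + 2 + 8 = 28 weeks. This matches the stated participation of 28 weeks.

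**Windows.** Count days from the last session of a period and let M be the days in a month. The documents do not define a month, so M = 28 to 31 is an assumption.

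- T1 window (section 5.1, footnote h): day 0 to M.
- 8-week assessment (Visits 11 and 22): day 56 − M to 56 + M.
- Largest active-sham difference in T1 timing within one participant: M − 0 = M.
- Largest overlap of the two windows: M − (56 − M) = 2M − 56.

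| M | T1 window | Visit 11/22 window | Largest T1 difference | Overlap |
|---|---|---|---|---|
| 28 | 0–28 | 28–84 | 28 days | 0 days |
| 30 | 0–30 | 26–86 | 30 days | 4 days |
| 31 | 0–31 | 25–87 | 31 days | 6 days |

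With real calendar months, for every Friday last session in 2022–2023 (104 illustrative dates), the overlap is 3 to 6 days. It needs T1 at the late end of its window and the 8-week visit at the early end of its own. With the 8-week visit on its nominal day 56, the latest T1 is still 25 to 28 days earlier.

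**If T1 is held to the last day**, as sections 6.2 and 6.6 state, the active-sham timing difference is 0 days and the 8-week visit is at least 25 days later.

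**Illustration of size.** The documents give no training gain and no decay rate. Assume a 10-point gain in both periods, no stimulation effect, and exponential decay with half-life h days. The fraction left at day d is 2^(−d/h). With T1 at day 0 in one period and day d in the other, the false difference is 10 × (1 − 2^(−d/h)).

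| Half-life | Fraction left at day 30 | False difference, day 0 v day 30 | False difference, day 0 v day 7 |
|---|---|---|---|
| 2 weeks (14 d) | 0.23 | 7.7 points | 2.9 points |
| 4 weeks (28 d) | 0.48 | 5.2 points | 1.6 points |
| 8 weeks (56 d) | 0.69 | 3.1 points | 0.8 points |
| 16 weeks (112 d) | 0.83 | 1.7 points | 0.4 points |

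Day 0 against day 30 is the worst case. If both T1 days were independent and uniform on days 0–30 (a further assumption), the mean gap is 30/3 = 10 days. The mean absolute false difference is then 2.5, 1.7, 1.0 and 0.6 points for the four half-lives.

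**The case against.** The two accounts can be read as a target and a tolerance: sections 6.2 and 6.6 name the intended day, and section 5.1 allows later completion. The 2-week time frame may simply describe the length of treatment. That is a fair reading, but it does not say which delay the analysis assumes, and a tolerance of a month in each period still needs a matching rule or an adjustment.

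Section 3.1 criticises an earlier trial's 2-month washout because gains persisted at the 2-month follow-up. This fits poorly with a 2-week half-life and points to the lower end of the illustrated range. Most battery tests are also not practised, so a training gain of this kind applies mainly to the trained items. Both points stand, and they limit the size of the problem.

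The SAP's first tests, Cochran's Q and McNemar, are run within a condition, and the T0-T1 contrast is given as an example. That is so, but it is the comparison that the SAP describes as the direct one between treatment conditions.

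Three stronger readings are tempting and are not supported.

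- **Systematic bias towards one condition.** Staff who deliver stimulation and assess language are blinded, so the delay should be unrelated to condition. The problem is uncontrolled error within a person.
- **Immediate and retained effects cannot be told apart.** The overlap with Visits 11 and 22 is about 4 days, only at opposite extremes. The visit numbers imply an order, although no rule enforces a gap.
- **The planned regression of language on connectivity is undermined.** The only such model written out, in section 6.5, uses baseline connectivity, so a gap between post-treatment scan and battery does not enter it.

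**Conclusion.** The Protocol contradicts itself on when T1 is measured, and the visit schedule as written lets T1 differ by up to about 30 days (28 to 31) between a participant's active and sham periods. That difference enters the SAP's within-participant contrast with no matching or adjustment. With one period of each condition per person, timing and condition cannot be separated for that person.

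The window arithmetic rests only on the length of a month. The point sizes rest on an assumed gain, an assumed form of decay and the most extreme pair of dates. They show that scheduling alone could produce 1.7 to 7.7 points, not that it did. The documents give no actual assessment dates, so whether any participant was affected is unknown. The overlap with the 8-week visits is a secondary point. The matter should be corrected, but it does not by itself invalidate the comparison.

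**What to change.** **Protocol, for any further enrolment or a later trial.** Reconcile section 5.1 and Table 1 footnote h with sections 6.2 and 6.6. Set a narrow post-treatment assessment window, for example days 0 to 7 after the last session, for battery, MRI and MEG. Require the same interval in both periods of a participant to within a few days. State a minimum gap between T1 and Visits 11 and 22.

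**SAP, for data already collected.** The SAP is written in the past tense, so new windows cannot help these data. List the actual days of T0, T1 and T2 relative to treatment, by participant and condition. T0 belongs in the listing because it may fall up to 3 months before each period and enters the same change score. Repeat the active-sham contrast without pairs whose T1 intervals differ by more than a stated limit, for example 7 days. That limit is a judgement and should be labelled as one. If too few pairs remain, report the listing and qualify the contrast.

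**Cost.** Wording in two sections and one table footnote, one listing and one sensitivity analysis. The downside is tighter MRI and MEG booking, some out-of-window visits, and fewer pairs in a sensitivity analysis of an already small sample.

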Secondary Objectives	(ii) evaluate the effects of HD-tDCS on functional connectivity using functional Magnetic Resonance Imaging (fMRI), and (iii) elucidate its effects on spontaneous neuronal oscillatory patterns using Magnetoencephalography (MEG).
Endpoints	
 • Primary outcome measurements: Language performance changes as assessed at baseline and after tDCS stimulation procedures (time frame: 2 weeks). • Secondary outcome measurements: (ii) Changes in brain functional connectivity as assessed at baseline and after tDCS stimulation (time frame: 2 weeks) (iii) Changes in abnormal patterns of neuronal frequencies and synchronizations as assessed at baseline and after tDCS stimulation procedures (time frame: 2 weeks).

Study Design	
This clinical utility study is a randomized, double-blind, sham-controlled trial in which stimulation or sham will be administered to 20 subjects over the age of 45 years, with the order of treatments counterbalanced in a within-subject crossover design. Stimulation and sham sessions last 20 minutes and occur for 10 days over a 2-week period.
 
The study consists of Pre-screening (Visit –1), Baseline (Visit 1), a 2-week Treatment Period (Visits 1-10), a 16-week Washout Period, an Interim Assessment (Visit 11), a second 2-week Treatment Period (Visits 12-21), and a Final Assessment (Visit 22).

Study Agent/ Intervention Description	tDCS and sham stimulation sessions lasting 20 minutes at a current intensity of up to 2mA in the targeted cortical tissue
Number of Subjects	20
Subject Participation Duration	28 weeks: 2 weeks of tDCS/sham, followed by a 16-week washout, followed by 2 weeks of tDCS/sham, followed by an 8-week final assessment.
Duration of Follow up	None
Estimated Time to Complete Enrollment	18 months
Statistical Methodology	The collection of pilot data from this study will provide initial estimates of the variability and the effect sizes. This information will then be used for the more formal calculations of power and sample size necessary to conduct a pivotal trial. All future statistical testing will use repeated measures ANOVA once a large enough sample is reached.
Safety Assessments	Data safety monitoring board meetings will be scheduled to monitor progression of the study and review drug adverse events

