5.4.5. Neuroimaging Assessments

The acquisition strategy for IvPPA participants is to collect datasets that include resting-state functional MRI (rs-fMRI), diffusion MRI (dMRI), and resting state magnetoencephalography (rsMEG).

MRI Acquisition Protocols

All IvPPA patients will undergo four 60-minute 3T MRI scanning sessions (total 4 hrs), including high-resolution T1 and T2 structural MRI, dMRI, and rs-fMRI as summarized below. In the case of left handed participants (approximately 80% are left hemispheric dominant), they will undergo a quick fMRI test (~ 6 min) to confirm their left hemispheric dominance (Binder et al. 1995).

3T MRI Hardware: Scanning will be done on GE MR 750 3T clinical scanners (50 mT/m & 200 T/m/s gradients) with a Nova 32-channel neuroimaging phased array receive head coil and whole-body rf transmission.

3T MRI Pulse Sequences: fMRI and diffusion MRI acquisitions will use prototype GE pulse sequences from the "ProtoPak2" software package, made available to us by a research agreement with GE. These state-of-the-art sequences provide multi-band acquisition of fMRI and dMRI data, greatly accelerating the acquisitions and allowing reductions in voxel size and repetition time to match those of the HCP protocol.

Resting-State fMRI (rs-fMRI) Protocol. The rs-fMRI parameters will be identical to the HCP Lifespan protocol, including an eyes-open fixation task, 30 minutes of rs-fMRI data divided into six 5-minute runs, and a 50:50 alternation of phase encoding direction.

Structural MRI Protocol. T1-weighted structural images will be acquired using the GE "BRAVO" pulse sequence and "Cube" with "ARC" for T2-weighted images, which is a 3D fast spin echo sequence using GE's autocalibrated parallel imaging technology. These vendor-supplied sequences provide comparable image quality to those of the HCP at the same 0.8 mm isotropic voxel size.

Prior to fMRI scans, subjects will undergo MRI safety screening and, as detailed in sections 7.3. and 7.4., respectively.

MEG Acquisition Protocol

MEG offers relatively good spatial localization of neural activity sources together with millisecond temporal resolution not possible with hemodynamic imaging methods. All IvPPA patients will undergo resting state MEG recordings.

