Define $\widetilde{LG}(s, g, t) \equiv Res(s, g, t)$. We will test the residuals $\widetilde{LG}(s, g, t)$ using a *three-factor crossed-nested* ANOVA, with fixed factors *group* and *time*, and random factor *subject* nested within *group*. We will test for group and time main effects, as well as the group \times time interaction. If we find significant main effects or interactions, we will perform post hoc procedures to determine which time and group combinations are significantly different.

6.4. Functional-Connectivity Changes Due to Stimulation. We will use the well established Human Connectome Project (HCP) fMRI processing pipelines implemented by [name] group at MCW, which include state-of-the-art noise removal, spatial normalization, and surface-based cortical parcellation methods.

Functional connectivity matrices will be computed by first parcellating the brain into multiple regions of interest (ROI), averaging the preprocessed fMRI signal over each ROI, and then computing the Z-transformed correlation coefficient between every ROI pair. The functional connectivity of a number of different parcellation schemes will be examined. This includes anatomical atlas based parcellation, such as the Harvard Oxford atlas, a validated probabilistic atlas implemented in FSL that divides each hemisphere into 56 regions corresponding to portions of cortical gyri and subcortical gray matter nuclei; combined anatomical and functional parcellation of regions that tend to co-activate during resting state, as implemented in Statistical Parametric Mapping (Tzourio-Mazoyer, N., et al., 2002) and purely functional delineations such as the Crad-200, a constrained spectral clustering of resting state fMRI data into 200 parcels encompassing both cortical and subcortical regions, and a high model order Independent component analysis (ICA), as advocated by HCP investigators. Targeted exploration of connectivity driven by current understanding of the pathophysiology of IvPPA will also be pursued.

We will employ age, years of education, gender, and gray matter (GM) volume as time-invariant covariates to obtain residual variables to determine LFC changes due to stimulation. We will model the LFC as a function of these nuisance regressors, using the following multiple linear regression equation, and retain the residuals as $LFC_{Res}^+(s, t)$ for further analysis:

$$LFC(s, t) = \beta_0 + \beta_1 Age(s) + \beta_2 Edu(s) + \beta_3 GM(s) + \beta_4 Gender(s) + Res(s, g, t)$$

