where $\widetilde{LFC}^+(s, g, t) \equiv Res(s, g, t)$. This regression will be performed using all of the data (i.e., all subjects, all groups, and all times). We will test the residuals $\widetilde{LFC}^+(s, g, t)$ using *three-factor crossed-nested analysis of variance* (ANOVA), with fixed factors of *group* and *time* and a random factor of *subject* nested within *group* (i.e., all subjects will be tested at all times, but the sham and stimulation groups will contain different treatment phases). We will test for both group and time main effects, as well as for the group \times time interaction. If we find significant main effects or interactions, we will perform post hoc procedures to determine which time and group (i.e., sham Vs. stimulation) combinations are significantly different.

6.5. Prediction of Changes in Correlation Between LFC and LG Before and After tDCS. A multiple linear regression is used to model LG as a linear function of LFC and test the difference in slope and intercept between the active stimulation and sham groups. If the subject is in the active stimulation group, $A(s, g) = 1$; if the subject is in the sham (placebo) group, $A(s, g) = 0$.

$$LG(s, g) = \beta_{0,0} + \beta_{0,1}A(s, g) + \beta_{1,0}LFC(s) + \beta_{1,1}LFC(s)A(s, g) + Res(s)$$

Here, **LFC(s)** represents baseline LFC for subject s (for simplicity, nuisance regressors are not shown).

6.6. Changes in Spontaneous Neuronal Oscillatory Patterns and synchronizations due to Stimulation

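### Sections 6.2 and 6.4 give the fMRI ANOVA's group and time factors inconsistent meanings; only a reading that 6.2 does not state (time as period, outcome as within-period change) validly tests stimulation

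*Protocol*

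**What the plan says.** Protocol 6.2 sets up the notation. Index g denotes two 10-patient groups, described as "subject groups, both of which will receive both sham and active tDCS at different treatment phase", which is treatment order. Index t has two values. Data are taken at baseline "and on the last day of each 2-week treatment period. These two time points will be denoted" t = 1, 2. There is no index for period or for treatment.

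Protocol 6.4 regresses LFC on age, education, gray matter volume and gender, using all the data. It tests the residuals in an ANOVA with fixed group and time and with random subject nested within group. It explains the nesting by saying that "all subjects will be tested at all times, but the sham and stimulation groups will contain different treatment phases". Post hoc tests are to find which "time and group (i.e., sham Vs. stimulation) combinations are significantly different". Both phrases make group look like condition.

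The design is a crossover: 5.4.5 (Randomization, Treatment Dosing and Administration) has all patients switch treatment in period 2. Patients "will undergo four 60-minute 3T MRI scanning sessions (total 4 hrs" in all, and 5.1 has them "receive MRI, MEG, and Language Battery on visits 12 and 21", so each period has its own pre- and post-treatment scan.

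Section 6.5 gives each patient one treatment code A and one baseline LFC. Section 6.6 carries the fMRI regression models over to MEG without naming the ANOVA.

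Two statements bear on whether the ANOVA is still intended. The Protocol Summary says: "All future statistical testing will use repeated measures ANOVA once a large enough sample is reached". The SAP, dated July 2023 against May 2022 for the protocol, says that the small sample ruled out group-level analysis. It then describes language tests only.

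**The concern.** In a two-period crossover, the stimulation effect is the contrast between a patient's two periods. A model that labels only group and pre/post can isolate it only if one of those labels carries period or treatment. Section 6.2 assigns neither label that role. Section 6.4 assigns treatment to group, but keeps a nesting that belongs to order: a patient can be nested in an order, but not in a condition when every patient has both.

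Two competent analysts could therefore fit different models from the same text. One model's interaction test cannot respond to stimulation. The other's standard error is right only in a special case. Sections 6.4 to 6.6 hold the only group-level imaging analysis in the documents, so nothing elsewhere settles the matter. The SAP does not describe an imaging analysis.

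**Working it through.** **Inputs from the documents:** 20 patients, 10 per order (6.2); randomization in blocks of 4; four MRI sessions per patient. **Assumed, because the documents give no values:** SD of a within-period pre-post change = 1; active-minus-sham effect d = 0.7 or 0.5 SD; correlation r between a patient's two changes from -0.3 to 0.7; two-sided 5% tests (the SAP gives p < 0.05 for its language tests; 6.4 gives no level). The plan states no figure to reproduce.

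**Model.** Change in period p = m + k_p + d (if active) + error, where m is practice or decline and k_p is the period effect.

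**Reading A: g is order, t is pre/post pooled over periods.**
- Active-first mean change: m + (k1 + k2)/2 + d/2.
- Sham-first mean change: m + (k1 + k2)/2 + d/2.
- Group x time = d/2 - d/2 = 0. This is algebra and needs no assumed value beyond no carryover into the second change. In simulation it rejects 5% of the time at every r, despite d = 0.7.
- The time effect keeps d/2 (0.35 when d = 0.7), added to m and the mean period effect. At r = 0.5 it is significant about 40% of the time with d = 0.7 and no practice gain, and also about 40% with d = 0 and a practice gain of 0.35 SD. It cannot tell the two apart.

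**Reading B: g is condition, subject nested.** Group x time compares 20 active with 20 sham changes as if they came from 40 people (38 df). With balanced orders and no carryover the estimate is d, so it is unbiased. Its true variance is 2(1 - r)/20, while the nested test assumes 2/20. The ratio of true to assumed standard error is sqrt(1 - r). The comparator is a two-sample t on period differences between orders (18 df). Simulated results without a period effect:

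| r | sqrt(1 - r) | Nested: type I error | Nested: power, d = 0.7 | Period differences: power, d = 0.7 | Nested: power, d = 0.5 | Period differences: power, d = 0.5 |
|---|---|---|---|---|---|---|
| -0.3 | 1.14 | 8.5% | 57% | 45% | 35% | 26% |
| 0 | 1.00 | 5.0% | 58% | 55% | 34% | 32% |
| 0.3 | 0.84 | 2.1% | 59% | 71% | 31% | 43% |
| 0.5 | 0.71 | 0.8% | 61% | 84% | 29% | 56% |
| 0.7 | 0.55 | 0.1% | 64% | 97% | 25% | 78% |

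The period-difference test has 5% type I error throughout. The nested test's higher power at r = -0.3 comes with its inflated type I error. Leaving out period also matters: with second-period changes lower by 1 SD, nested type I error at r = 0 falls to about 3%.

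If the orders are unequal, reading B is biased by k x (sham-first - active-first)/N, where k = k2 - k1. With k = -0.5 SD and 10 active-first, 6 sham-first: -0.5 x (6 - 10)/16 = 0.125 SD with no true effect. Blocks of 4 balance 20 patients, but dropout or early stopping can undo that.

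**Reading C: g is order, t is period, outcome is the within-period change.**
- Active-first: period 1 minus period 2 = (k1 - k2) + d. Sham-first: (k1 - k2) - d.
- Half the difference is d, free of m and of the period effect. Subject nested in order is then correct.
- Group x time is the same test as the period-difference t: in one simulated data set F and t squared were both 6.919 (18 df).

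**Which reading fits the notation?** The index ranges give 10 x 2 x 2 = 40 values. Planned scans are 20 x 4 = 80; within-period changes are 20 x 2 = 40. Reading B needs 20 x 2 x 2 = 80. Reading A fits 40 only if scans are averaged over periods, which is not stated. The count therefore favors C, but 6.2's wording of t favors A and 6.4's wording of group favors B.

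**The case against.** The strongest reply is that reading C is what was meant. The 40 slots fit it. Section 6.3 prints a Delta before LG, and 6.4 introduces "time-invariant covariates to obtain residual variables to determine LFC changes due to stimulation". Under C each order-by-period cell is either sham or stimulation, so the remark in 6.4 could describe the cells and not the group factor. The printed 6.4 equation has no Delta, but its indices are irregular in the text as read, so a missing symbol is weak evidence. All this stands as support for C. It does not settle the matter, because 6.2 never defines t as period and its two time points begin with baseline.

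The second reply is that the ANOVA is probably no longer operative, given the Protocol Summary's condition and the SAP's sentence. This lowers the practical weight. It does not close the point, because the SAP does not mention fMRI or MEG and does not say that 6.4 is withdrawn.

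A reader might also infer more than the documents support:
- *That every reading of the plan fails.* Reading C does not.
- *That the stimulation effect vanishes under reading A.* It vanishes from group x time; the time effect keeps half of it, confounded.
- *That the nested test inflates false positives.* It does so only if a patient's two changes are negatively correlated, and the documents give no reason to expect that. With positive correlation it is conservative.
- *That power is lost by a known amount.* As r rises, nested power rises at d = 0.7 and falls at d = 0.5, so even the direction depends on an assumed effect.
- *That the MEG analysis has the same flaw.* Section 6.6 names regression models only, so extending the ANOVA to MEG is an inference.

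**Conclusion.** The inconsistency is real and is in the current text. Taken literally, 6.2 gives an interaction test that cannot detect stimulation (absent carryover). The condition reading of 6.4 gives an unbiased estimate when orders are balanced and there is no carryover, but with an error term that is about right only at zero correlation without a period effect. One reading is valid, and it is partly supported but not stated.

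The cancellation under reading A is exact. Every error rate and power figure rests on assumed inputs and illustrates size only. Section 6.5 has a related ambiguity: each patient has both conditions and two pre-treatment scans (visits 1 and 12), yet gets one treatment code and one baseline LFC.

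This should be fixed, as a definition that is missing and not as proof that the intended analysis is wrong. Its practical weight is limited if the imaging ANOVA was dropped, but that needs to be said.

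**What to change.** - **6.2:** define order (g), period and treatment as separate indices.
- **6.4:** state that the outcome is the within-period pre-post change in LFC and that t is period. Estimate active minus sham by comparing period differences between orders (N - 2 df), with a 95% confidence interval. Order x period with subject nested in order, or fixed patient, period and treatment effects, gives the same test. Delete the parenthesis that equates group with sham against stimulation.
- **6.5:** code A by period, use that period's baseline LFC, and account for patient and period.
- **6.6:** state whether the 6.4 test applies to MEG.
- **SAP:** state whether the sentence on group-level analysis withdraws the imaging ANOVA. If it does, say that imaging is reported per patient without group tests.

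A description of the visit 12 minus visit 1 difference by order, as a look at carryover, is optional.

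The cost is wording and model code; the scans are already scheduled. The drawback is precision if few patients are enrolled. With equal orders the half-width is t(0.975, N - 2) x sqrt(2(1 - r)/N). At an assumed r = 0.5 this is 2.101 x sqrt(1/20) = 0.47 SD for 20 patients, 2.306 x sqrt(1/10) = 0.73 SD for 10, and 4.303 x sqrt(1/4) = 2.15 SD for 4. At the low end, per-patient reporting may be the more honest choice.
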